5.4.3 Clinical Laboratory Data

The following clinical laboratory parameters are assessed in the protocol:

- Hematology: Complete blood count with differential and platelet count, INR, prothrombin time, and APTT
- Blood chemistry: total protein, albumin, creatinine, blood urea nitrogen, uric acid, bilirubin (total and direct), alkaline phosphatase, alanine aminotransferase, aspartate aminotransferase, gamma-glutamyl transferase, glucose, calcium, phosphorus, bicarbonate, chloride, sodium, and potassium
- Urinalysis: dipstick for blood, protein, and glucose (microscopic examination may also be performed)

- [REDACTED]

- [REDACTED]

- [REDACTED]

	Statistical Analysis Plan Placebo-Controlled Period	V1.0
---	---	-------------

All the laboratory tables and listings, unless otherwise specified, will be presented by treatment group.

5.4.3.1 Quantitative laboratory analyses

For numeric laboratory parameters, actual values, change and percent change from baseline will be summarized by visit. Number of evaluable subjects, mean, standard deviation, median, min and max values will be presented at each visit.

Plots of mean values (with standard deviation) for key numeric laboratory parameters by visit will be provided.

Visit windows for by visit summaries

For laboratory by visit summaries, the analysis visit should be defined using visit windows in Appendix II. If there is more than 1 value in the same analysis visit window (>1 value for the same analysis visit) for a certain parameter for a subject, then the closest record to the target visit day will be used for the by visit analysis. If there are 2 values in the same analysis visit window with the same distance from the target visit day for a certain parameter for a subject, then the record with the later date will be used for the by visit analysis. If there are 2 values on the same day for a certain parameter for a subject, then the record with the later time will be used for the by visit analysis. If there are 2 records on the same date and time, then use the average value for quantitative parameters and the worse value for qualitative parameters.

5.4.3.2 Qualitative laboratory analyses

For all qualitative analyses, all values will be included (not just the “analyzed record” within each visit window in the quantitative analyses).

Shift analyses

Laboratory data will be summarized using shift tables where appropriate. Each subject’s hematology, blood chemistry and urinalysis numeric values will be flagged as “low”, “normal”, or “high” relative to the normal ranges of the central laboratory or as “unknown” if no result is available. Each subject’s urinalysis categorical values will be flagged as “positive”, “negative”, or “unknown” if no value is available. Shifts from baseline to high/low status will be presented for hematology, blood chemistry and urinalysis numeric parameters, and shifts from baseline to abnormal (positive) will be presented for urinalysis categorical parameters.

In the hematology, blood chemistry and urinalysis numeric values shift summary tables, entries are numbers of subjects shift to low (or high) divided by number of subjects at risk

CONFIDENTIAL

The information contained herein may not be used, disclosed, or published without the written consent of Biogen MA Inc.

followed by corresponding percentages. Number at risk for shifting to low (or high) is the number of subjects whose baseline value was not low (or high) and who had at least one post-baseline evaluation. Shift to low includes normal to low, high to low, and unknown to low. Shift to high includes normal to high, low to high, and unknown to high.

In the urinalysis categorical values shift summary table, entries are numbers of subjects shift to abnormal (positive) divided by number of subjects at risk followed by corresponding percentages. Number at risk for shift to abnormal (positive) is the number of subjects whose baseline value was not abnormal (positive) and who had at least one post-baseline evaluation. Shift to abnormal (positive) includes normal or negative to positive and unknown to positive.

Potentially Clinically Significant (PCS) laboratory abnormalities analyses

For hematology, blood chemistry and urinalysis, the number of subjects with potentially clinically significant laboratory abnormalities post-baseline will be summarized for the parameters provided in [Table 5.1](#). Subjects need to have at least one post-baseline evaluation in order to be included in the analysis.

Listings will also be presented for all subjects with any PCS laboratory abnormalities. In these listings, each subject's complete history from screening to last study visit for that specific laboratory test meeting the PCS criteria will be listed; any abnormal values based on the normal ranges of the central laboratory and abnormal values based on PCS criteria will be separately flagged in the same listing.

Table 5.1. Criteria to Determine Potentially Clinically Significant (PCS) Laboratory Abnormalities

Clinical Laboratory Outlier Criteria			
Parameter name	PCS Low	PCS High	STANDARD UNIT in the SDTM dataset
HEMATOLOGY			
Basophils Absolute	N/A	>1.6 x 10 ⁹ /L	10 ⁹ /L
Eosinophils	N/A	>1.6 x 10 ⁹ /L	10 ⁹ /L
Erythrocytes (RBC)	≤3.5 x 10 ¹² /L	≥6.4 x 10 ¹² /L	10 ¹² /L
Hematocrit - Females	≤0.32	≥0.54	L/L
Hematocrit - Males	≤0.37	≥0.60	L/L
Hemoglobin - Females	≤95 g/L	≥175 g/L	g/L
Hemoglobin - Males	≤115 g/L	≥190 g/L	g/L
Leukocytes (WBC)	<3.0 x 10 ⁹ /L	>16 x 10 ⁹ /L	10 ⁹ /L
Lymphocytes	<0.8 x 10 ⁹ /L	>12 x 10 ⁹ /L	10 ⁹ /L
Monocytes	N/A	>2.5 x 10 ⁹ /L	10 ⁹ /L
Neutrophils	<1.5 x 10 ⁹ /L	>13.5 x 10 ⁹ /L	10 ⁹ /L
Platelet count	≤75 x 10 ⁹ /L	≥700 x 10 ⁹ /L	10 ⁹ /L
BLOOD CHEMISTRY			
Albumin	≤25 g/L	≥625 g/L	g/L
Alkaline phosphatase (ALP)	N/A	>3 x ULN	IU/L
Alanine aminotransferase (ALT)	N/A	>3 x ULN	U/L
Aspartate aminotransferase (AST)	N/A	>3 x ULN	IU/L
Bicarbonate	≤16 mmol/L	≥35 mmol/L	mmol/L

CONFIDENTIAL

The information contained herein may not be used, disclosed, or published without the written consent of Biogen MA Inc.

Clinical Laboratory Outlier Criteria			
Parameter name	PCS Low	PCS High	STANDARD UNIT in the SDTM dataset
Bilirubin	N/A	>1.5 x ULN	umol/L
Calcium	≤2 mmol/L	≥3 mmol/L	Mmol/L
Chloride	≤90 mmol/L	≥118 mmol/L	Mmol/L
Creatinine	N/A	≥176.8 umol/L	Umol/L
Gamma-Glutamyl Transferase	N/A	>3 x ULN	U/L
Glucose	≤2.2 mmol/L	≥9.7 mmol/L	Mmol/L
Potassium	≤3 mmol/L	≥6 mmol/L	Mmol/L
Phosphate	≤0.6 mmol/L	≥1.7 mmol/L	Mmol/L
Protein	<45 g/L	≥100 g/L	g/L
Sodium	≤126 mmol/L	≥156 mmol/L	Mmol/L
Urate	N/A	>475.88 umol/L (female); >594.85 umol/L (male)	umol/L
Urea Nitrogen	N/A	≥10.7 mmol/L	Mmol/L
URINALYSIS			
Glucose	N/A	Trace or ≥ ++++	
Protein	N/A	Trace or ≥ ++	
Occult Blood	N/A	Trace or ≥+	
ULN = upper limit of normal			

Potential serious hepatotoxicity

Potential serious hepatotoxicity is defined as ALT or AST > 3x ULN and total bilirubin > 2x ULN at any time post-baseline, not necessarily concurrent. A scatterplot of the maximum post-baseline ALT or AST value relative to ULN and maximum post-baseline total bilirubin value relative to ULN (not necessarily concurrent) will be provided. In addition, a line plot of ALT, AST, ALP and total bilirubin values over time for each subject with potential serious hepatotoxicity will be provided. .

A listing of subjects with potential serious hepatotoxicity will be provided with the concurrent records labeled. Concurrent is defined as on the same day. Subjects with ALT > 1x ULN, > 3x ULN, > 5x ULN, > 10x ULN or > 20x ULN, subjects with AST > 1x ULN, > 3x ULN, > 5x ULN, > 10x ULN or > 20x ULN, subjects with total bilirubin > 1x ULN, >1.5x ULN or > 2x ULN, subjects with ALP >1x ULN or >1.5x ULN, and subjects with AST or ALT > 3x ULN post-baseline accompanied by concurrently elevated total bilirubin > 1.5x ULN or > 2x ULN will be labeled.

5.4.4 Vital Sign Data

Vital sign parameters include diastolic blood pressure, systolic blood pressure, body temperature, pulse rate and respiration rate. Vital signs will be measured with the subject supine and after the subject has been resting for at least 10 minutes. The analysis of vital signs will focus on the incidence of clinically relevant abnormalities based on the following criteria in [Table 5.2](#).

Table 5.2. Criteria Used to Clinically Relevant Abnormalities in Vital Signs

Variable	Low	High
Body temperature	<36 degrees C	>38 degrees C
Pulse Rate	<60 bpm	>100 bpm
Systolic Blood Pressure (Supine)	<90 mm Hg or a decrease from baseline of >30 mm Hg	>140 mm Hg or an increase from baseline of >40 mm Hg
Orthostatic Systolic Blood Pressure	> 20 mm Hg decrease from supine to 3-minute standing measure	
Diastolic Blood Pressure	< 50 mm Hg or a decrease from baseline of > 20 mm Hg	≥90 mm Hg or an increase from baseline of >30 mm Hg
Orthostatic Diastolic Blood Pressure	>10 mm Hg decrease from supine to 3-minute standing measure	
Respiration Rate	< 12 breaths per minute	>20 breaths per minute
Weight	≥7% decrease from BL	≥7 % increase from BL
BL= baseline; bpm = beats per minute		

Note: the clinically relevant abnormality criteria will be evaluated based on the supine measure unless otherwise mentioned.

A summary table for subjects with any clinically relevant post-baseline abnormalities will be provided. In the summary table, entries are numbers of subjects with an abnormality divided by number of subjects evaluated followed by corresponding percentages. Number evaluated is the number of subjects who had a baseline assessment and at least one post-baseline assessment for that vital sign.

The descriptive statistics for actual values and change from baseline will be summarized over time for each treatment group and overall active group. The line of mean vital sign over time by treatment group will be graphed.

A subject listing will be presented for subjects with any post-baseline clinically relevant abnormalities in vital signs. In this listing, each subject's complete vital sign values from screening to last study visit will be listed with abnormalities labeled.

Visit windows for by visit summaries

For vital sign visit summaries, the analysis visit will be defined by visit window in Appendix II. For the same parameter for a subject, if there is more than 1 record in the same analysis visit window), then select the record closest to the target visit day. If there are 2 records in the same analysis visit window with the same distance from the target visit day, then select the record with the later date. If there are 2 records on the same date, then use the average value for quantitative parameters and the worse value for qualitative parameters.

5.4.5 ECG Data

Actual value and change from Baseline in ECG will be summarized using descriptive statistics and presented by treatment group, overall active group and visit.

The ECG result is classified as normal or abnormal. The post baseline abnormal ECG result is further classified as abnormal AE or Abnormal but not AE. Shift table from normal or

CONFIDENTIAL

The information contained herein may not be used, disclosed, or published without the written consent of Biogen MA Inc.

unknown ECG at baseline to abnormal post-baseline ECG will be summarized. The worst post-baseline record of each subject is selected. Subjects with abnormal post-baseline ECG status will be listed.

In addition, the number of subjects with potential QTcF interval outlier post-baseline will be summarized by treatment group. The criteria of defining QTcF interval outliers is specified in [Table 5.3](#).

Table 5.3. Criteria used for QTcF interval outlier

Variable	Low	High
QTcF interval (msec.)	NA	>450; >480; >500
Increase in QTcF interval (msec.)	NA	>30; >60

Visit windows for by visit summaries

For ECG visit summaries, the analysis visit will be defined by visit window in Appendix II. For the same subject, if there is more than 1 record in the same analysis visit window, then the record closest to the target visit day is selected. If there are 2 records in the same analysis visit window with the same distance from the target visit day, then the record with the later date is selected. If there are 2 records on the same date, then the worse record is selected.

5.4.6 Physical and Neurological Examination

Abnormal findings during physical and neurological examinations are captured as adverse events and will be reflected in the summary of AEs.

5.4.7 C-SSRS Data

The Columbia Suicide Severity Rating Scale (C-SSRS) is an assessment that evaluates suicidal ideation and behavior. C-SSRS measurements are collected with respect to “Lifetime: time he/she felt most suicidal” and “P3M: time he/she felt most suicidal during the past 3 month” at baseline, and with respect to “Since last visit” at post-baseline visit.

There are 11 common “Yes/No” questions at baseline and post-baseline visits. Five questions on *suicidal ideation* and five questions on *suicidal behavior* are re-ordered and follow increasing severity order respectively as shown in [Table 5.4](#); another question on *self-injurious behavior without suicidal intent* is listed separately. In particular, only subjects who answered “Yes” to question 2 will proceed to question 3, 4 and 5, and the questions in the section of intensity of ideation. Thus, for any subjects who answered “No” to question 2, an answer “No” will also be assumed to question 3, 4, and 5. An additional “Yes/No” question is used to record if subject had committed suicide in post-baseline visits.

Table 5.4: C-SSRS re-ordered questions

Suicidal Ideation	
Question 1	Wish to be dead
Question 2	Non-specific active suicidal thoughts

CONFIDENTIAL

The information contained herein may not be used, disclosed, or published without the written consent of Biogen MA Inc.

	Statistical Analysis Plan Placebo-Controlled Period	V1.0
---	---	-------------

Question 3	Active suicidal ideation with any methods (not plan) without intent to act
Question 4	Active suicidal ideation with some intent to act, without specific plan
Question 5	Active suicidal ideation with specific plan and intent
Suicidal Behavior	
Question 6	Preparatory acts or behavior
Question 7	Aborted attempt
Question 8	Interrupted attempt
Question 9	Actual attempt
Question 10	Suicidal behavior
Question 11 (post-baseline visits only)	Suicide
Self-Injurious Behavior without Suicidal Intent	
Question 12	Self-injurious behavior without suicidal intent

A subject is considered to have *suicidal ideation* at the period of interest if a “Yes” is answered to any of the five suicidal ideation questions (Question 1-5). A subject is considered to have *suicidal behavior* at the period of interest if a “Yes” is answered to any of the five suicidal behavior questions (Question 6-10) at baseline or a “Yes” is answered to any of the six suicidal behavior questions (Question 6-11) at post-baseline visit.

A subject’s *Suicidal Ideation Score* is defined as the maximal suicidal ideation question number (maximal of 1-5) with an answer “Yes” per visit. The score is defined as 0 if the subject answered “No” to all 5 Suicidal Ideation questions at that visit.

The following analyses on C-SSRS measurements will be conducted:

- Descriptive summary of subjects who answered “Yes” to any question 1-12 as well as subjects who had suicidal ideation or suicidal behavior at baseline and at any post-baseline visit. the denominator for summary is the number of subjects who were dosed and had a baseline assessment and at least one post-baseline assessment for each question.

Listing of subjects having a post-baseline suicidal ideation will be provided. The listing will display both baseline and post-baseline suicidal ideation scores for each subject.

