4.5.7 C-SSRS Data

The Columbia Suicide Severity Rating Scale (C-SSRS) is an assessment that evaluates suicidal ideation and behavior. There are 5 “Yes/No” questions on suicidal ideation following the increasing severity order: (1) Wish to be dead, (2) Non-specific active suicidal thoughts, (3) Active suicidal ideation with any methods (not plan) without intent to act, (4) Active suicidal ideation with some intent to act, without specific plan, (5) Active suicidal ideation with specific plan and intent, and 6 “Yes/No” questions on suicidal behavior

CONFIDENTIAL

The information contained herein may not be used, disclosed, or published without the written consent of Biogen MA Inc.

	Statistical Analysis Plan Dose Blinded Extension Period	V2.0
---	--	-------------

following the increasing severity order: (6) Preparatory acts or behavior, (7) Aborted attempt, (8) Interrupted attempt, (9) Actual attempt, (10) Suicidal behavior, (11) Suicide (only at post-baseline visits). Another “Yes/No” question of whether the subject has engaged in non-suicidal self-injurious behavior is also collected.

The summary table for C-SSRS will be conducted for the active treatment (placebo-controlled and DBE) period. Number of subjects who answered “Yes” to each of the 11 questions post-baseline, subjects who answered “Yes” to at least one question for suicidal ideation, subjects who answered “Yes” to at least one question for suicidal behavior, and subjects who have engaged in non-suicidal self-injurious behavior will be presented.

A listing of subjects with any suicidal ideation or behavior at baseline or post-baseline will be provided for the placebo-controlled and DBE period.

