As this study is on-going when the Covid-19 public health emergency (PHE) occurred, subject visits and data collection were impacted, including missing visits, delayed visits, missed assessments and/or some visits were performed via remote assessments, e.g. telephone/video visits. Every effort was made to document these impacted study activities systematically on the eCRF and other electronic source data.

CONFIDENTIAL

The information contained herein may not be used, disclosed, or published without the written consent of Biogen MA Inc.

	Statistical Analysis Plan Dose Blinded Extension Period	V2.0
---	--	-------------

A complete listing of all visits impacted (e.g. missed visits, delayed or assessment done via remote visits) will be listed in the clinical study report. Missing data due to Covid-19 is considered as missing at random.

Impact of COVID-19 on the clinical outcome analyses

In addition, subgroup analyses of the selected key clinical outcome MDS-UPDRS will be performed on a subset of subjects who did not have ≥ 3 consecutive missing doses throughout the study to further evaluate the impact of Covid-19 on the study. The same MMRM model for the primary analyses will be used for the subgroup analyses.

In addition, due to Covid-19, some visits were delayed. A few subjects will have their Week 52 imaging done at later visits up to Week 72 and these will still be considered as Week 52 visit data in the analyses for Week 52. These data were not included in the Week 52 database lock in time, but will be included in the Week 72 database, and the related Week 52 imaging analyses will be updated at the time of the Week 72 interim analyses.

Impact of COVID-19 on the safety analyses

During the COVID-19 pandemic period, subjects may be prone to a high risk of getting depressed or anxiety. As a result, the analyses below will be performed to evaluate the impact of the COVID-19 pandemic on the safety analyses.

1. An overall summary of AE in DBE period based on data after March 7th, 2020, the start date when subjects in SPARK get impacted by COVID-19
2. An overall summary of AE in the active treatment (placebo-controlled and DBE) period based on data after March 7th, 2020, the start date when subjects in SPARK get impacted by COVID-19
3. AEs by system organ class and preferred term sorted by decreasing frequency in DBE period based on data after March 7th, 2020, the start date when subjects in SPARK get impacted by COVID-19

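### The C-SSRS tables never compare a subject with his or her own baseline, and two Year 1 rules (the Question 11 denominator and the ideation-only listing) need repair

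*SAP*

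**What the plan says.** **Year 1 SAP, Section 5.4.7.** At baseline the C-SSRS is asked for two look-back periods, lifetime and the past 3 months. At later visits it covers the time since the last visit. Questions 1-5 are ideation, 6-11 behaviour, and 12 self-injury without suicidal intent. Table 5.4 labels the suicide item "Question 11 (post-baseline visits only". After baseline, behaviour means a positive answer to "any of the six suicidal behavior questions (Question 6-11) at post-baseline visit". A Suicidal Ideation Score from 0 to 5 is defined per visit.

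One analysis is planned: a descriptive summary of positive answers to Questions 1-12, together with "subjects who had suicidal ideation or suicidal behavior at baseline and at any post-baseline visit". I read this as two separate counts. The denominator is the "number of subjects who were dosed and had a baseline assessment and at least one post-baseline assessment for each question".

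On listings: "Listing of subjects having a post-baseline suicidal ideation will be provided". Also: "The listing will display both baseline and post-baseline suicidal ideation scores for each subject".

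**DBE SAP, Section 4.5.7.** The table counts post-baseline positives for each of 11 questions, for any ideation, for any behaviour, and for self-injury. On listings: "A listing of subjects with any suicidal ideation or behavior at baseline or post-baseline will be provided"; the sentence goes on to cover both the placebo-controlled and the extension period.

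**DBE SAP, Section 5.** During the pandemic "subjects may be prone to a high risk of getting depressed or anxiety", and a further C-SSRS summary on data after 7 March 2020 is planned in response.

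**The concern.** Year 1 is the only placebo-controlled period, so it is where the arms can be compared on suicidality that arises on treatment. That comparison needs each subject set against his or her own starting point. The plan does this for other safety data: laboratory values, ECG and MRI all get shifts from baseline (Year 1 SAP Sections 5.4.3.2, 5.4.5 and 5.4.8), and adverse events are analysed by treatment emergence (Section 5.4.2). The C-SSRS tables do not, although the ideation score that would allow it is already defined.

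Two Year 1 rules also give an undefined or incomplete output if a programmer follows them to the letter: the denominator for the suicide item, and the trigger for the listing.

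**Working it through.** The C-SSRS sections state no rate, sample size or power, so there is no planned figure to reproduce. The check is mostly logical.

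**1. Item count.** 5 ideation + 5 behaviour + 1 self-injury = 11 items common to all visits; adding suicide after baseline gives 12. This agrees with the Year 1 summary of Questions 1-12 and with the DBE count of 11 plus self-injury. There is no error here.

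**2. What separate baseline and post-baseline counts cannot show.** Take two hypothetical arms of 101, the size of the three larger arms in Year 1 SAP Table 4.2.

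- Arm X: 5 subjects answer yes to Question 1 at baseline, and the same 5 do so afterwards.
- Arm Y: 5 subjects answer yes at baseline and not again; 5 other subjects answer yes for the first time afterwards.

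The Year 1 table is identical for both: 5/101 = 5.0% at baseline and 5/101 = 5.0% after. The DBE layout would show 5 post-baseline in each. Among the 101 − 5 = 96 subjects without baseline ideation, new onset is 0/96 = 0% in X and 5/96 = 5.2% in Y.

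**3. Size, under assumptions only.** The documents give neither baseline prevalence nor onset rates. Assume 5% to 10% baseline ideation that persists, and 2% to 4% new onset.

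| Arm size (Table 4.2) | Persistent, unchanged | New onset |
|---|---|---|
| 101 | 0.05 × 101 = 5.1 to 0.10 × 101 = 10.1 | 0.02 × 101 = 2.0 to 0.04 × 101 = 4.0 |
| 54 (250 mg) | 0.05 × 54 = 2.7 to 0.10 × 54 = 5.4 | 0.02 × 54 = 1.1 to 0.04 × 54 = 2.2 |

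Under these assumptions unchanged cases would outnumber new ones in the ideation row. With lower baseline prevalence or less persistence they would not.

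**4. Which baseline.** Section 5.4.7 collects two baseline look-backs and does not say which one supplies the baseline count. Even the side-by-side counts are therefore not fully defined.

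**5. Question 11 denominator.** The rule asks for a baseline and a post-baseline assessment for each question. Nobody has a baseline answer to Question 11, so the literal denominator is 0 and the percentage is undefined. If the phrase about each question belongs to the post-baseline assessment only, the row can be computed, but the wording does not settle which is meant. On either reading, a subject with no baseline form drops out even with a later attempt, and so does a subject who dies before any post-baseline form. By contrast, the laboratory, ECG and MRI shift tables keep subjects whose baseline is unknown.

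**6. Where each kind of subject appears.**

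| Subject, post-baseline | Year 1 summary | Year 1 listing | DBE listing |
|---|---|---|---|
| Ideation score 1, unchanged | Question 1 and ideation rows | Yes, both scores | Yes |
| Ideation score from 1 to 5 | Question 5 and ideation rows | Yes, both scores | Yes |
| Attempt, no ideation | Question 9 and behaviour rows | No | Yes |
| Suicide, no ideation, both assessments present | Behaviour row; Question 11 percentage undefined if literal | No | Yes |

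**The case against.** The case against is strong on several points, and most of it stands.

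- A reader might infer that completed suicide is excluded from the Year 1 output. It is not. Suicide is among the summarised Questions 1-12 and in the Question 6-11 composite. Section 5.4.2 also gives a death row in the adverse event overview, a listing of deaths, and serious adverse events by system organ class and preferred term. What remains is an unusable denominator for one row.
- A reader might infer that treatment-emergent suicidality is not reported at all. That goes too far. Suicidality recorded as an adverse event is analysed as treatment-emergent, including worsening of a pre-existing condition, and the Year 1 listing shows baseline and later ideation scores together.
- A reader might infer that the tables treat a post-baseline score of 1 and a score of 5 alike. They do so only in the any-ideation row. The per-question rows separate them, but still do not show who changed.
- A reader might infer that behaviour without ideation is lost. It is in the Year 1 summary, and the DBE listing covers it for the placebo-controlled period. It is missing only from the Year 1 listing.
- The remark on depression concerns the pandemic, and the DBE SAP responds with an extra C-SSRS summary. It gives context and does not show a defect, although that summary is not described as comparing subjects with baseline either.
- Persistence is not automatic, because later forms ask only about the time since the last visit. Eligibility rules, which may limit baseline suicidality, are in the protocol, which is not at hand.

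These points narrow the matter but do not remove it. Adverse event reports depend on an investigator recording an event, and a listing gives no rate by arm. Neither replaces a table from the instrument itself.

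**Conclusion.** The point holds in a limited form. Neither SAP tabulates new or worsened ideation, or new behaviour, by arm from the C-SSRS. The Year 1 baseline look-back is not named. Read literally, the Year 1 denominator is empty for Question 11. The Year 1 listing omits subjects with behaviour and no ideation, in conflict with the DBE listing for the same instrument.

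The documents do not support saying that completed suicide is excluded or that emergent suicidality goes wholly unreported. The size of any masking cannot be derived from them; the 5% to 10% and 2% to 4% rates are illustrative assumptions. The denominator finding rests on the literal reading, and under the other reading it is an ambiguity. This is a matter of descriptive safety reporting, not of clinical management. It should be corrected, but it does not touch the primary analysis.

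**What to change.** 1. In Year 1 SAP Section 5.4.7, state which baseline look-back, lifetime or past 3 months, is used for comparison.
2. In both SAPs, add one table by treatment group: subjects whose maximum post-baseline Suicidal Ideation Score exceeds their baseline score, and subjects with new behaviour, with a shift of baseline against maximum post-baseline score. For delayed-start subjects, use the DBE baseline already defined in DBE SAP Section 4.1. Note that, for the C-SSRS, the last form before the first extension dose covers only the time since the previous visit.
3. For Question 11 and the behaviour composite, drop the requirement for a baseline answer. Use dosed subjects with any post-baseline C-SSRS or a death record as the denominator.
4. Extend the Year 1 listing to any post-baseline ideation or behaviour, in line with DBE SAP Section 4.5.7.

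The cost is some SAP wording and one added table per SAP, all from data already collected.
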